Each morning during the eight-week intervention, participants will receive questions about their current affect, intent to engage in physical activity, and self-efficacy for engaging in physical activity. At each request, participants will be given the option to “snooze” the request for up to one hour. The assessment questions will be viewed and responded to on the Fitbit Versa device. We will utilize the Fitbase Engage platform (see Figure 3), which utilizes the Fitbit SDK to deliver assessments and message prompts via the Fitbit Versa. Assessment questions have been validated for their use in EMA.⁵⁻⁷ Daily questions will include:

Figure 3. Representations of messages delivered via the Fitbase Engage platform.

*Actual messages will be customized as described below.

Physical Activity Intention (One item; 1 strongly disagree to 5 strongly agree)

“I intend to meet my goal of XXX steps today”

Physical Activity Self-Efficacy (One item; 1 not confident at all to 5 completely confident)

“I believe I can complete my goal of XXX steps today.”

Affect (Nine items assessing positive and negative affect; 1 not at all to 5 extremely)

“How (happy, cheerful, relaxed, stressed, anxious, angry, depressed, energetic, fatigued/tired) do you feel right now?”

Affective Framing Messages. After completing the daily EMAs, participants may receive an affective framing message. Message delivery will occur on a 1:1 randomization schedule, such that participants will receive messages on 28 of the 56 intervention days. The study biostatistician will generate randomization schedules for each participant using block randomization with variable block sizes. Messages will be randomly selected from a pool of 14 messages, meaning each message will be received twice during the eight-week study. Messages will emphasize potential improvements in mood, energy, and calmness.^{8,9} Examples of these messages:

“Research has shown that physical activity often results in improved mood.”

“Most people report feeling happier and more relaxed after exercise.”

Weekly Goal Setting. Each Sunday evening, participants will receive a prompt to select a step goal for the upcoming week. Along with this prompt, participants will receive feedback on their activity during the previous week. Participants will receive either: 1) the average daily number of steps taken during the previous week, or 2) the highest daily number of steps taken during the previous week.

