Intention Planning Prompts. Delivery of these messages will occur on a 1:1 randomization schedule, such that participants will receive messages on 28 of the 56 intervention days. Planning prompts will be delivered in the evening at a time preferred by the participant. At each request, participants will be given the option to “snooze” the request for up to one hour. Using a drop-down

menu, participants will be able to indicate the time, duration, and location to complete the following prompt:

“Tomorrow, at (time), I will walk for (duration) minutes at (location).”

Activity recognition. We will utilize Fitbit SmartTrack feature to automatically detect physical activity bouts. The SmartTrack settings will be customized to identify all physical activity bouts of ≥ 10 minutes. Approximately one hour after completion of a physical activity bout, participants will be asked to report on their current affect and reflect upon their experience during the physical activity bout. Delivery of these assessments will occur after each activity bout; however, in the event of multiple activity bouts occurring in one day, assessments will be limited to the first activity bout of that day. Participants will be given the option to “snooze” for up to one hour if they are unavailable.

Affect (Nine items assessing positive and negative affect; 1 not at all to 5 extremely)

“How (happy, cheerful, relaxed, stressed, anxious, angry, depressed, energetic, fatigued/tired) do you feel right now?”

Remembered Experience (One item; 1 very good to 5 very bad).

“Think back to how you felt during your physical activity today - How do you remember feeling?”

Savoring – After completing the EMAs, participants will receive the savoring messages after 50% of their detected activity bouts (1:1 randomization schedule). Participants will receive imagery-based prompts, as those have been shown to elicit more positive affect responses compared to descriptive prompts (Nelis et al 2015). Delivery of the savoring prompts will occur over approximately 1-minute, with pauses interspersed between prompts to allow for the participant to imagine their experience (see below).

“Thinking back to that physical activity bout, try to create an image of that in your mind. Spend a moment re-living the activity.”

(10 seconds)

“Replay that memory as if you were watching a movie in mind.”

(10 seconds)

“What could you see around you?”

(10 seconds)

“What could you hear?”

(10 seconds)

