A repeated-measures mixed effects model will be used as described in Klasnja et al. (2015) with participant and time as random effects and other effects as fixed. Daily step count will be the dependent variable while main effects of affective framing intervention (message/no message) and linear time effects will be within-subjects factors, and an intervention by time interaction term will be included. We also will consider more complex effects of time (e.g., quadratic effects). We will include scores of the Physical Activity Intention, Physical Activity Self-Efficacy, and Affect as time-varying covariates. As described in Klasnja, et al. (2015) we will include the scores for the day prior to the intervention so the covariates will not be affected by the intervention. We will also classify each day as a cancer treatment day (i.e. day on which chemotherapy or radiation therapy is received) or not and presence/absence of cancer treatment will also be a time-varying covariate. A time lag is not needed for this covariate as the timing of cancer treatment will not be influenced by the intervention. Presence/absence of an implementation planning message on each day will also be included as a time-varying covariate and an affective framing by planning message interaction will be included to assess synergistic effects of the two messages. The baseline measurement of theoretical moderators of physical activity behavior change (Physical Activity Stage of Change, Physical Activity Self-Efficacy, Multidimensional Outcome Expectations for Exercise Scale) and psychosocial characteristics Functional Assessment of Cancer Therapy – General, Quick Inventory of Depressive Symptomatology – Self-Rated, Brief Fatigue Inventory) will be considered as covariates as will other baseline demographic and clinical variables determined to improve the fit of the final model.

Hypothesis 2b: *Participants will have greater daily step counts on days receiving the implementation planning message compared to non-message days.*

The same repeated-measures mixed effects model described for Hypothesis 2a will be used for this hypothesis. Only the interpretation of the results will be different as the presence/absence of the implementation message will be the main effect and the affective framing intervention will be considered the covariate.

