Hypothesis 2c: Participants randomized to receive feedback prompts reporting their highest daily step count will achieve greater step counts compared to participants that receive feedback prompts reporting their average daily step counts.

Participants will be randomized at baseline for the duration of the study because we expect that the intervention will have a cumulative effect over the course of the study. The hypothesis will be tested using a repeated-measures mixed effects model with participant and time as random effects and other effects as fixed. Daily step count will be the dependent variable. The intervention (highest vs average steps feedback) will be a between-subjects factor and time the within-subjects factor and an intervention by time interaction term will be included. We also will consider more complex effects of time (e.g., quadratic effects). The baseline characteristics described in Hypothesis 2a will be considered to improve the fit of the final model. We will also consider the inclusion of time-varying covariates if a clinically meaningful imbalance between groups is found.

Exploratory analyses

For Aim 2a and 2b we will also evaluate the moderating effects of time-varying factors measured through daily EMA (Physical Activity Intention, Physical Activity Self-Efficacy, and Affect). Our ultimate goal is to be able to evaluate these factors to inform decision rules in the ultimate adaptable intervention. The proposed sample size limits the power to detect time-varying moderators of intervention effects and formal analysis of moderating effects will only be conducted in the subsequent clinical trial. These analyses will use a repeated-measures mixed effects model as described above for Hypotheses 2a and 2b, and the moderating effect will be represented by a 3-way interaction of intervention, covariate, and time.

Power calculations

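### For the framing message only, the one-day lag on the EMA scores is unnecessary: the same-morning score already precedes the message, and the lag weakens the exploratory framing moderator analyses

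*Combined protocol and SAP*

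**What the plan says.** Section 7.0 (Hypothesis 2a) puts the daily intention, self-efficacy and affect scores into the mixed model as time-varying covariates, one day back: "we will include the scores for the day prior to the intervention so the covariates will not be affected by the intervention". The contrast drawn for cancer-treatment days confirms that a true lag is meant: "A time lag is not needed for this covariate as the timing of cancer treatment will not be influenced by the intervention". Hypothesis 2b reuses that model: "The same repeated-measures mixed effects model described for Hypothesis 2a will be used for this hypothesis". The model also holds the planning message and a framing-by-planning interaction.

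Section 5.4 fixes the order of events. For the EMA: "Each morning during the eight-week intervention, participants will receive questions about their current affect, intent to engage in physical activity, and self-efficacy". For framing: "After completing the daily EMAs, participants may receive an affective framing message". The intention item is about the current day ("I intend to meet my goal of XXX steps today"), as is the self-efficacy item, and the affect items ask about the present moment. For planning: "Planning prompts will be delivered in the evening at a time preferred by the participant". The planning text concerns a walk on the following day.

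The exploratory part of section 7.0 tests the EMA scores as moderators for both 2a and 2b. It refers back to the models above without restating the lag. The longer-term aim it gives is to "evaluate these factors to inform decision rules in the ultimate adaptable intervention". It also says that power for moderators is limited and leaves their formal analysis to a later trial.

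**The concern.** The reason given for the lag is to keep the covariates clear of the intervention. For framing, the schedule in section 5.4 already does this: on any day the EMA is answered before a framing message can arrive. The lag therefore adds no protection for that contrast. It replaces the participant's state at the decision point, including two items about today's goal, with a state about a day old.

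Two things are at stake, both limited. In 2a, an older covariate explains less of the day's step variance. In the framing moderator analyses, the question changes from whether this morning's state alters the response to this morning's message to whether yesterday's state does. A just-in-time rule would act on the former.

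There are small side effects too. Day 1 has no prior-day score. Because goals are reset on Sunday evening, Monday's lagged intention and self-efficacy scores refer to the previous week's goal. That touches two of the eleven items and leaves the covariates pre-treatment.

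**Working it through.** **1. Order of events.** Take the steps on day t, with each planning prompt matched to the day it talks about.

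| Event | When | Same-morning EMA (day t) | Prior-day EMA (day t−1) |
|---|---|---|---|
| Framing message | morning of day t, after the EMA | before it | before it |
| Planning prompt | evening of day t−1 | after it | before it |

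For framing both scores are pre-treatment, and the same-morning one is closer to the decision. For planning only the prior-day score is pre-treatment.

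**2. The plan's own figure.** Section 7.0 gives N = 50 for a standardized effect of 0.109, with 56 days, randomization probability 0.5, 80% power and alpha 0.05. The noncentrality is N·T·p(1−p)·d² = 50 × 56 × 0.25 × 0.109² = 8.32. A two-sided F test with 1 and N−1−q degrees of freedom (q = 1, 2 or 3 nuisance parameters) gives power of about 0.81. The same formula returns every row of the 2a/2b table (17, 50, 60, 70, 100). No EMA score enters it, so this point leaves N = 50 unchanged.

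**3. Precision of the 2a main effect.** Let R² be the share of within-person step variance explained by the same-morning EMA, and r the day-to-day EMA correlation. Neither is in the documents. The lagged score explains R²r², so the detectable effect grows by √[(1 − R²r²)/(1 − R²)].

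| R² (assumed) | r = 0.8 | r = 0.2 |
|---|---|---|
| 0.05 | 1.009 | 1.025 |
| 0.10 | 1.020 | 1.052 |
| 0.20 | 1.044 | 1.114 |

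This is the 1% to 11% range. In simulation the 2a main effect averaged 0.107 to 0.110 with either score, against a true 0.109, so there is no bias.

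**4. Framing moderation.** If the effect varies with the current score by γ per SD, and the score follows a first-order autoregression, the expected coefficient on yesterday's score is rγ. The simulation used 50 people × 56 days, 800 runs per setting, γ = 0.109, independent daily draws and a within-person model with a message-by-score term.

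| r (assumed) | r × 0.109 | Mean estimate, same-morning / lagged | Power, same-morning / lagged |
|---|---|---|---|
| 0.2 | 0.022 | 0.107 / 0.024 | 77% / 10% |
| 0.5 | 0.055 | 0.109 / 0.054 | 81% / 29% |
| 0.8 | 0.087 | 0.110 / 0.088 | 82% / 62% |

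The shrinkage by r follows from the assumptions. The power figures depend on the chosen γ and on the score having no stable between-person part. If half its variance is stable between people and scores are not person-centred, the overall day-to-day correlation is 0.5 + 0.5r, which is 0.65 to 0.85 for within-person r of 0.3 to 0.7. Lagged power is then roughly 40% to 70%. These runs also use a two-way term, whereas section 7.0 plans a three-way term with time.

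**5. Counter-check for planning.** Assume a direct effect of 0.05, an EMA-to-steps slope of 0.2, and an evening prompt that shifts the next morning's EMA by c. The total effect is 0.05 + 0.2c.

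| c (assumed) | Total effect | Adjusted for same-morning EMA | Adjusted for prior-day EMA |
|---|---|---|---|
| 0.1 | 0.07 | 0.048 | 0.068 |
| 0.3 | 0.11 | 0.049 | 0.110 |
| 0.5 | 0.15 | 0.049 | 0.150 |

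The same-morning score removes the part of the planning effect that runs through the EMA. The prior-day score does not.

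**The case against.** The strongest defence is that 2a and 2b share one model, which also carries the framing-by-planning interaction. In that model a prior-day score is a coherent single choice, because it precedes both randomized components. This stands for planning, as step 5 of the working shows, provided the evening prompt is matched to next-day steps. It is why a blanket swap to same-morning scores would repair 2a and damage 2b. It does not make the lag necessary for framing.

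The plan also credits the lag to a cited methods paper. Whether that paper is applied correctly cannot be checked here. The point rests only on the order of events in section 5.4.

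A reader might infer three stronger things that the documents do not support:

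- That the lag biases the 2a test. It does not; the cost is precision alone.
- That the lag is wrong in every moderator model. Those for planning need a pre-prompt score.
- That the trial's purpose is defeated. The stated aims are feasibility, acceptability and component effects. The moderator work is exploratory with acknowledged low power, no power is claimed for it, and no confirmatory conclusion depends on it.

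Limited power is still no reason to give up more of it when a better-timed score is already being collected.

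**Conclusion.** The point holds for the framing message only, as an inexpensive improvement. The stated reason for the lag does not apply to framing under the protocol's own schedule.

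For Hypothesis 2a the loss is small and concerns precision. For the exploratory framing moderators, an effect acting through the current state is estimated at about r times its size. This assumes that only the current state moderates; if yesterday's state matters in its own right, the loss is smaller. Since r, the between-person share and the size of any moderation are all absent from the documents, the power figures show direction and should not be quoted as the trial's power.

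One further gap has to be closed for any version of the covariate rule to work. Hypothesis 2b speaks of steps on days when a planning message is received, while the prompt is sent in the evening about the next day. Matched to the calendar day of delivery, most of the steps could precede the prompt, and the last EMA before it would be that same morning's. The plan needs to say which day is meant.

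**What to change.** Amend section 7.0 before analysis:

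- **Hypothesis 2a and the framing moderators:** use the same-morning EMA completed before the framing message, citing the order in section 5.4. Planning may stay in this fit as a covariate, but its effect is not read from it.
- **Hypothesis 2b, its moderators and the framing-by-planning interaction:** use the last EMA completed before the planning prompt, and read these effects only from this fit.
- **Day alignment:** state that an evening prompt is matched to the next day's steps, as its wording implies. The last pre-prompt EMA is then the prior day's relative to those steps.
- **Moderator section:** state the EMA timing for each component instead of leaving it to cross-reference, and say how days with a missing EMA are handled.

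The cost is wording and two fits in place of one shared model. No new data are needed and the sample size does not change.

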5.4 Treatment and Study Intervention

Participants will receive a Fitbit Versa and instructions on its use. Participants will be asked to wear the device for eight weeks, removing it only for charging and when engaging in activities in which the device could be submerged in water beyond its recommended depths (water resistant up to 50 meters).

Manual Connection and Pre-Authorization: At baseline, a research staff member will create a unique email and password combination in order to create an account on Fitbit.com.

During the account creation process the following information will be entered:

- First Name: A de-identified placeholder name will be entered
- Last Name: A de-identified placeholder name will be entered
- Date of Birth: The first day of the month of birth will be entered OR The first day of the year of birth will be entered.
- Gender/Sex: The participant's gender will be entered.
- Height: The participant's height will be entered.
- Weight: The participant's weight will be entered.

It is important to note that the personal demographic details - date of birth, gender, height, and weight - are required for accurate estimation of data captured by the Fitbit Device.

The Fitbit account will be connected to a research device. Once the device is connected to the study-generated and study-controlled Fitbit account it will be manually connected to the Fitabase platform and assigned a unique study ID so that data will be synced and available for viewing and downloading by research staff. All data associated with the Fitbit device will be linked to the chosen unique study ID in the Fitabase platform.

Participants will be given the connected Fitbit device and be provided with the associated email/password so that they may login into the Fitbit.com user account, use the online dashboard, and associated mobile applications. They will be informed that research staff will be able to access, view, and download their data through the Fitabase platform. The participant will be given a copy of the Fitabase Terms of Use and the Privacy Policy for review during the consent process. By consenting to use the Fitbit device as part of this study the participants also signals an acceptance of the Fitabase Terms of Use and Privacy Policy.

At enrollment, participants will indicate a preferred time to receive affective framing messages and EMA prompts (morning), and intention planning prompts (evenings).

Ecological momentary assessment.

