6.1.1 Study Assessments

At baseline and at the end of the eight-week intervention, participants will complete assessments of: 1) potential moderators of physical activity behavior change, and 2) psychosocial outcomes.

Primary outcome measurement:

Fitbit Versa. The primary outcome measure will be daily step counts measured by the Fitbit Versa. Wrist-worn Fitbit devices demonstrate acceptable reliability and validity for measuring step counts.¹³ We will utilize Fitabase, a comprehensive data management platform that utilizes the Fitbit partner-level API, to capture near real-time participant activity data.

Theoretical moderators of physical activity behavior change:

Physical Activity Stages of Change Questionnaire: 4-item scale that assesses current stage of activity.

Physical Activity Self-Efficacy Questionnaire: 3-item scale that assesses self-efficacy for physical activity.

Multidimensional Outcome Expectations for Exercise Scale: 15-item scale that assesses a multitude expectations for physical activity.

Affective associations: 6-item scale that assesses feelings about exercise.

Affective attitudes: 3-item scale that assesses feelings during exercise.

Anticipated affect: 2-item scale that assesses the anticipated affect of regular physical activity.

Psychosocial Outcomes:

Functional Assessment of Cancer Therapy: 19-item scale that assesses quality of life in cancer patients.

Quick Inventory of Depressive Symptomatology – Self-Rated (QIDS-SR): 16-item scale that assesses severity of depression-specific symptoms.

Brief Fatigue Inventory (BFI): 9-item scale that assesses fatigue in cancer patients

Generalized Anxiety Disorder 7 item Scale (GAD-7): 7-item scale that assesses anxiety symptoms.

Pittsburgh Sleep Quality Index (PSQI): 19-item scale that assesses sleep quality and disturbances.

Pain – Frequency, Intensity, and Burden Scale (P-FIBS): 4-item scale that assesses the frequency, intensity, and burden of pain.

Dimensional Anhedonia Rating Scale (DARS): 21-item scale that assesses anhedonia.

Exercise Vital Sign (EVS): 2-item scale that assesses an estimate of an individual's physical activity.

Intervention Acceptability:

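### Hypothesis 2b tests steps on the day of an evening prompt that plans the next day's walk, so the analysis will miss a real effect and may reverse its sign

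*Combined protocol and SAP*

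**What the plan says.** **Timing of the prompt (section 5.4).** At enrolment, "participants will indicate a preferred time to receive affective framing messages and EMA prompts (morning), and intention planning prompts (evenings"). The intention planning paragraph repeats this: "Planning prompts will be delivered in the evening at a time preferred by the participant". The participant completes the sentence "Tomorrow, at (time), I will walk for (duration) minutes at (location"). The framing message is a morning message and the planning prompt an evening one, about the day to come.

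**Outcome (section 6.1.1).** "The primary outcome measure will be daily step counts measured by the Fitbit Versa".

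**Hypothesis and model (section 7.0, Aim 2).** Hypothesis 2b states: "Participants will have greater daily step counts on days receiving the implementation planning message compared to non-message days". The model is written out under Hypothesis 2a, where "Presence/absence of an implementation planning message on each day will also be included as a time-varying covariate", together with a framing-by-planning interaction. Under 2b: "The same repeated-measures mixed effects model described for Hypothesis 2a will be used for this hypothesis"; only the interpretation changes.

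**Lags.** The 2a paragraph lags the daily EMA (ecological momentary assessment) covariates: "we will include the scores for the day prior to the intervention so the covariates will not be affected by the intervention". It also explains why the cancer-treatment indicator needs no lag. It gives no lag for the planning indicator.

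**The concern.** A same-day contrast suits 2a, because the framing message arrives in the morning and that day's steps follow it. It does not suit 2b. By the time the planning prompt arrives, the day's step count is largely fixed, and the walk being planned belongs to the next day. The model codes that next day by its own evening prompt, which is randomised separately. The coefficient labelled as the planning effect is then mostly a comparison of steps taken before the prompt.

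This is the only test of the planning component's main effect. Section 1.0 says that acceptability and efficacy results will determine which components enter the adaptive intervention, so a false null here counts against a component that may work.

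The interaction meant to show synergy has the same fault: it pairs a morning framing message with a prompt not yet sent. The exploratory moderator analyses for 2b reuse the model and inherit the problem.

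**Working it through.** **Inputs from the plan (section 7.0, Power calculations, and section 5.4).** N = 50 people; T = 56 days; probability of a prompt p = 0.5 each day; alpha = 0.05 (taken as two-sided, since sidedness is not stated); 80% power; constant standardised effect d = 0.109.

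**Step 1: reproduce the plan's sample size.** The noncentrality is N·T·p(1-p)·d² = 50 × 56 × 0.25 × 0.109² = 700 × 0.01188 = 8.32. An F test on 1 and N-q-1 degrees of freedom, with q from 1 to 3, gives power of 0.806 to 0.807. It returns 17, 50, 60, 70 and 100 people for effects of 0.200, 0.109, 0.099, 0.091 and 0.076, exactly as tabulated. The sample size is not in error; it assumes a prompt and an outcome that are correctly paired.

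**Step 2: what the same-day contrast estimates.** Assume that a prompt on the evening of day t raises steps on day t+1 by d and affects no other day. The same-day coefficient then has expectation d × r, where r is the correlation between prompt assignments on adjacent days.

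- Independent daily randomisation: r = 0.
- Exactly 28 of 56 days in random order: r = -1/55, so the expectation is -0.002.
- Permuted 1:1 blocks: two days in a block of size b correlate at -1/(b-1). Each block holds b-1 adjacent pairs, so it contributes -1 in total. Averaged over days, r is about -1/(mean block size).

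**Step 3: size.** The standard error with unit within-person SD is 1/√(N·T·p(1-p)) = 1/√700 = 0.0378. The chance of a significant benefit is P(Z > 1.96 - mean/SE), and of a significant harm P(Z < -1.96 - mean/SE).

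| Planning schedule | r | Mean same-day estimate | Significant benefit | Significant harm |
|---|---|---|---|---|
| Independent daily | 0 | 0.000 | 2.5% | 2.5% |
| Blocks 4/6/8 (assumed) | -1/6 | -0.018 | 0.7% | 7% |
| Blocks 2/4/6 (assumed) | -1/4 | -0.027 | 0.4% | 11% |
| Blocks of 2 (assumed) | -1/2 | -0.055 | under 0.1% | 30% |

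Simulation of 50 × 56 person-days with a within-person regression agrees. Under independent randomisation the mean was about 0.00, with a significant benefit in about 2% of trials. Blocks of 2/4/6 gave about -0.027 and 0.2%, and blocks of 4/6/8 about -0.018 and 1%.

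**Step 4: next-day coding.** Pairing each prompt with the following day's steps leaves 55 usable pairs. The noncentrality is 50 × 55 × 0.25 × 0.01188 = 8.17, and the F test has power 0.80. In simulation the mean estimate was 0.109 with power of about 81 to 82%.

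**Step 5: if some effect falls on the same evening (independent randomisation).** With 10% of the effect on the same day, mean/SE = 0.0109/0.0378 = 0.29 and power is P(Z > 1.67), about 5% (about 4% in simulation). With 25%, mean/SE = 0.0273/0.0378 = 0.72 and power is P(Z > 1.24), about 11%.

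**The case against.** **Reversal is not certain.** It needs the planning schedule to be blocked. Section 5.4 states blocking with variable sizes only under the framing messages, and the power section describes a 50% chance each day, which reads as independent randomisation. This stands: reversal is conditional on blocking. Missing the effect is not.

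**The outcome does not wholly precede the prompt.** Steps taken after the prompt count towards that day, and the plan gives neither a clock time nor the spread of steps within a day. This also stands, but Step 5 shows that a same-evening share of 10 to 25% leaves power at about 4 to 11%. Carry-over beyond the next day does not help under independent randomisation, because earlier prompts are unrelated to tonight's assignment.

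**The simulation assumes a next-day effect.** True, and its figures illustrate the fault rather than forecast the result. The assumption is the one the prompt's own wording makes.

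**No rule drops a component after a null result.** Correct: this is a pilot, inclusion rests on acceptability as well as efficacy, and a later trial is foreseen. The efficacy evidence for planning would still be uninformative.

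**The team may already mean the next day.** Possibly, and the data would support either coding. But the plan discusses lags for other covariates, gives none here, and never defines a message day as the day after the prompt. An analyst following the text would code the wrong day.

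**Conclusion.** The concern holds, and the plan must be corrected before analysis. As written, 2b relates evening prompts to steps mostly taken before them. If the effect is confined to the next day at 0.109 SD, with independent residuals within person, the chance of a significant benefit falls from the planned 80% to about 2% under independent randomisation, and to about 1% or less under the assumed blocked schedules. In the blocked case the estimate is also negative on average, by roughly one sixth to one half of the true effect. The sample size of 50 is unaffected and remains adequate once the prompt is paired with the following day.

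**What to change.** - Reword 2b to compare step counts on the day after an evening planning prompt with those on the day after an evening without one.
- In the shared 2a/2b model, define the planning indicator for day t as the randomised prompt status on the evening of day t-1. Use this lagged indicator in the main effect, the framing-by-planning interaction and the exploratory 2b moderator models. Leave the framing indicator on the same day.
- Keep the prior-day EMA covariates. The scores from the morning of day t-1 precede that evening's prompt, so they remain valid.
- State the handling of the ends. Day 1 has no preceding prompt and leaves the 2b contrast; say whether it stays in 2a, given that it also has no prior-day EMA score. The day-56 prompt has no following intervention day and drops out.
- State how the planning schedule is randomised, including whether it is blocked.
- Record the change before outcome data are analysed, so that the lag is not a post hoc choice.

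The cost is one reworded hypothesis, one lagged variable and one of 56 days per person (power 0.80 instead of 0.806). Data collection and conduct do not change.
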